1.2. Study Design

Design Configuration and Subject Population

GS-US-320-0108 is a randomized, double-blind, noninferiority study to compare the antiviral activity of TAF 25 mg versus TDF 300 mg for the treatment of HBeAg-negative, CHB in treatment-naïve and treatment-experienced subjects.

Treatment Groups

For non-China part, subjects were randomized in a 2:1 ratio to the following 2 treatment groups:

- **TAF group:** TAF 25 mg once daily + matched placebo of TDF 300 mg once daily (n = 285)
- **TDF group:** TDF 300 mg once daily + matched placebo of TAF 25 mg once daily (n = 141)

For China, approximately 150 subjects (100 in TAF group and 50 in TDF group) will be enrolled for local registration purposes.

Key Eligibility Criteria

Subjects were to have met the following key eligibility criteria:

- Documented evidence of chronic HBV infection (eg, HBsAg positive for more than 6 months)
- HBeAg-negative, CHB with the following: HBeAg-negative and HBeAb-positive at screening; screening HBV DNA $\geq 2 \times 10^4$ IU/mL; screening serum ALT level > 60 U/L (males) or > 38 U/L (females) and $\leq 10 \times$ ULN (by central laboratory range)
- Estimated creatinine clearance (CL_{Cr}) ≥ 50 mL/min (using the Cockcroft-Gault [CG] method) based on serum creatinine and actual body weight as measured at screening

Study Periods/Phases

The duration of randomized, double-blind treatment is 144 weeks (96 weeks under Amendment 1 and 2.1). At Week 144, all subjects remaining on blinded treatment will be switched to the open-label TAF 25 mg QD extension period for an additional 240 weeks (Week 144 through Week 384/ED). Subjects who already assigned to open-label phase at Week 96 per Amendment 2.1 and consented to Amendment 3.1 later will continue on open-label TAF 25 mg QD through Week 384/ED. All subjects who complete the double-blind period of treatment are eligible for participation in the open-label TAF 25 mg QD extension period. Subjects who permanently discontinue study drug (either prematurely [early discontinuation, ED] or at the end of study [Week 384]) for reasons other than HBsAg loss with confirmed seroconversion to anti-HBs will be followed every 4 weeks for 24 weeks off treatment or until initiation of alternative, commercially available HBV therapy, whichever occurs first.

Schedule of Assessments

Laboratory analyses (serum chemistry, liver tests, hematology, urinalysis, plasma HBV DNA levels, pregnancy testing [for females of childbearing potential]), vital signs, adverse events (AEs), and concomitant medications will be performed at screening, baseline, and every 4 weeks thereafter through Week 48, every 8 weeks through Week 96, every 12 weeks through Week 144, and every 24 weeks through Week 384/ED visit.

HBV serology (HBeAg, hepatitis B e antibody [HBeAb], HBsAg, and reflex hepatitis B surface antibody [HBsAb]) will be performed at screening and baseline, and HBsAg and reflex HBsAb will be performed every 12 to 16 weeks through Week 144, and every 24 weeks through Week 384 /ED, and at Follow up Weeks 12 and 24. Quantitative serum HBsAg will be assessed at screening, baseline, every 12-16 weeks until Week 144, every 24 weeks until Week 384/ED, and at all Follow Up visits. Bone and renal biomarker testing will be performed at baseline and then at defined intervals throughout the study. IL28B polymorphism genotype, HBV genotyping and vitamin D assessments will be performed at baseline only. FibroTest[®] will be performed at baseline, and every 48 weeks thereafter through Week 384/ED. Fasting metabolic assessments (fasting glucose and lipid panel) will be conducted at baseline, every 24 weeks until Week 144, and every 48 weeks until Week 384/ED visit.

Complete physical examinations will be performed at screening, baseline, and Weeks 24, 48, 72, 96, 120, 144, 240, and 384/ED. Symptom directed physical examinations including body weight assessment will be conducted at all other visits. Electrocardiogram (ECG) will be performed at screening and every 48 weeks thereafter. At sites in China with the capability only, dual energy x-ray absorptiometry (DXA) scans of the hip and spine will be conducted anytime during the screening period, and should be conducted at least 14 days prior to the first dose of study drug, and will be conducted every 24 weeks through Week 144, and every 48 weeks thereafter until Week 384/ED visit if not done within the last 24 weeks of ED visit. Hepatic ultrasound for surveillance of hepatocellular carcinoma will be performed starting at Week 96 and then every 24 weeks thereafter until Week 384/ED. Plasma, serum, and urine will be collected at baseline and at every visit thereafter for storage.

Follow-up assessments will occur every 4 weeks for 24 weeks and include the following: vital signs, hematology, serum chemistry, liver function tests, and plasma HBV DNA. Plasma, serum and urine will be collected for storage. HBsAg and reflex HBsAb will be evaluated at follow-up Weeks 12 and 24.

Ophthalmologic Substudy

For subjects who provide a separate informed consent (n = 30), a substudy will be conducted to assess ophthalmologic findings, including a fundoscopic examination with slit lamp and retinal photographs (both eyes) prior to the first dose of study drug and at Weeks 24, 48, 72, 96, and 144/ED visits at select sites. An exam should be performed at the ED visit if it is prior to Week 144 and not done within the last 24 weeks of this visit.

Randomization

Subjects will be randomized in a 2:1 ratio to the 2 treatment groups (TAF vs TDF, respectively). Randomization will be stratified by plasma HBV DNA level ($< 7 \log_{10}$ IU/mL, $\geq 7 \log_{10}$ IU/mL - $< 8 \log_{10}$ IU/mL, $\geq 8 \log_{10}$ IU/mL) and oral antiviral treatment status (treatment-naïve vs treatment-experienced).

Site and/or Stratum Enrollment Limits

Twenty-nine centers participated in China. There is no enrollment limit for individual sites.

Study Duration

The duration of the double-blind treatment is 144 weeks (96 weeks under Amendment 1 and 2.1). All subjects who complete the double-blind period of treatment are eligible for participation in the open label TAF 25 mg extension period for an additional 240 weeks (through Week 384/ED). Subjects already assigned to open label TAF 25 mg QD at Week 96 per Amendment 2.1 will continue on open label TAF 25 mg QD through Week 384/ED. Subjects who permanently discontinue study drug (either prematurely [ED] or at the end of study [Week 384]) for reasons other than HBsAg loss with confirmed seroconversion to anti-HBs will be followed every 4 weeks for 24 weeks off treatment or until initiation of alternative, commercially available HBV therapy, whichever occurs first. All subjects in China are currently enrolled under Amendment 3.1 and will complete 3 years of double-blind treatment before rolling over to open-label TAF 25 mg once daily.

Subjects with HBsAg loss with confirmed seroconversion to anti-HBs should discontinue study drug within 3-6 months following confirmation of seroconversion to anti-HBs. Subjects with HBsAg loss with confirmed seroconversion to anti-HBs prior to Week 48 are not permitted to discontinue study drug prior to the Week 48 visit. Subjects who discontinue study drug for confirmed seroconversion to anti-HBs will be followed off treatment every 4 weeks for 12 weeks and then per the study visit schedule through Week 384/ED. Discontinuation of study drug for subjects experiencing HBsAg loss with confirmed seroconversion, who have known bridging fibrosis or cirrhosis, should be considered on a case by case basis.

1.3. Sample Size and Power

For China, approximately 150 subjects (100 in TAF group and 50 in TDF group) will be enrolled for local registration purposes.

The sample size and power calculation described below was for non-China subjects. With respect to the primary efficacy endpoint of proportion of subjects with plasma HBV DNA levels below 29 IU/mL at Week 48, a sample size of 130 for the TDF group and 260 for the TAF group will have 90% power to rule out the noninferiority margin of 10% at a 1-sided significance level of 0.025. This assumes the expected difference (TAF – TDF) in proportion of subjects with HBV DNA < 29 IU/mL is 0 and the proportion of subjects with HBV DNA < 29 IU/mL in the TDF group is 91%. A similar response rate in the TDF group was observed in Study GS-US-174-0102.

This sample size (n = 260 for the TAF 25 mg group, n = 130 for the TDF 300 mg group) also provides the following:

- At least 90% power to detect a 1% difference in the percentage change from baseline in hip BMD at Week 48 (assuming a –1.17% change from baseline in TDF 300 mg group and –0.17% change from baseline in the TAF 25 mg group, with a common standard deviation (SD) of 2.20% and a 2-sided $\alpha = 0.025$)
- At least 77% power to detect a 1% difference in the percent change from baseline in spine BMD at Week 48 (assuming a –1.69% change from baseline in the TDF 300 mg group and -0.69% change in the TAF 25 mg group, with a common SD of 3.08% and a 2-sided $\alpha = 0.025$)
- At least 52% power to detect a 0.03 mg/dL difference in the change from baseline in serum creatinine at Week 48 (assuming a 0.04 mg/dL change from baseline in the TDF 300 mg group and 0.01 mg/dL change from baseline in the TAF 25 mg group, with a common SD of 0.12)

These assumptions above were derived from Studies GS-98-437, GS-98-438, GS-US-174-0102, GS-US-174-0103, and GS-US-174-0121.

2. TYPE OF PLANNED ANALYSIS

The Week 48 analysis for Non-China subjects was already conducted after the last subject completed the Week 48 visit or prematurely discontinued study drug. This statistical analysis plan (SAP) describes the analysis plan for the Week 48 analysis of subjects enrolled in China only.

2.1. Data Monitoring Committee (DMC) Analysis

An external multidisciplinary data monitoring committee (DMC) will review the progress of the study and perform interim reviews of safety data and provide recommendation to Gilead whether the nature, frequency, and severity of adverse effects associated with study treatment warrant early termination of the study in the best interests of the participants and whether the study should continue as planned or with modifications. The DMC may also provide recommendations as needed regarding study design.

The DMC will convene approximately every 24 weeks during the blinded portion of the study and approximately every 48 weeks during the open-label phase. More details are documented in the independent DMC charter.

2.2. Week 48 Analysis (Primary Analysis)

The Week 48 analysis will be conducted after the last subject completes the Week 48 visit or prematurely discontinues study drug.

Further analyses after Week 48 will be conducted if warranted.

3. GENERAL CONSIDERATIONS FOR DATA ANALYSES

3.1. Analysis Sets

Analysis sets define which subjects are included in an analysis. The assignment of subjects to analysis sets will be done before the study blind is broken for analysis. A summary of the number and percentage of subjects in each analysis set will be provided by treatment group and in total.

3.1.1. Randomized Analysis Set

The Randomized Analysis Set includes all subjects who were randomized into the study. This is the primary analysis set for by-subject listings.

3.1.2. Safety Analysis Set

The Safety Analysis Set includes all randomized subjects who have received at least 1 dose of study drug. Subjects will be analyzed according to the treatment they actually received during the double-blinded phase. This is the primary analysis set for safety analyses.

3.1.3. Full Analysis Set (FAS)

The FAS includes all randomized subjects who have received at least 1 dose of study drug. Subjects will be analyzed according to the treatment to which they were randomized during the double-blinded phase. This is the primary analysis set for efficacy analyses.

3.1.4. Per-protocol Analysis Set

The Week 48 Per-Protocol (PP) Analysis Set includes all subjects who (1) were randomized into the study, (2) had received at least 1 dose of study drug, and (3) had not been excluded based on criteria below. Subjects will be analyzed according to the treatment they actually received during the double-blinded phase. The PP analysis set is the secondary analysis set for efficacy analysis.

Subjects meeting any of the following criteria will be excluded from the Week 48 PP analysis set:

- Subjects who do not have on-treatment HBV DNA in the Week 48 analysis window, except for subjects who discontinue study drug due to lack of efficacy. (Note: lack of efficacy is defined as having the check-box for “Lack of Efficacy” marked as the reason for premature study drug discontinuation on the study drug completion electronic case report form [eCRF] page). The details are summarized in Table 3-1.

Table 3-1. Subjects Excluded from Week 48 PP Analysis Set Due to Premature Discontinuation and/or Missing HBV DNA Assessment in Week 48 Analysis Window

Discontinuation from Study Drug Prior to or on the Upper Bound of Week 48 Analysis Window		HBV DNA Data on Randomized Treatment Available in Week 48 Analysis Window	
		Yes	No
Yes	Due to Lack of Efficacy	+	+
	Due to Other Reasons	+	-
No		+	-

+ = Inclusion of Subjects in Week 48 PP analysis set; - = Exclusion of Subjects in Week 48 PP analysis set

- Subjects who meet the exclusion criterion for receiving ongoing therapy with any of the prohibited medications listed in the clinical study protocol (Section 4.3, Table 5.1).
- Subjects with adherence rate for active study drug up to the Week 48 visit below the 2.5th percentile.

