4.3. Exclusion Criteria

Subjects who meet any of the following exclusion criteria are not to be enrolled in this study.

1. Pregnant women, women who are breastfeeding or who believe they may wish to become pregnant during the course of the study.
2. Males and females of reproductive potential who are unwilling to use an “effective”, protocol-specified method(s) of contraception during the study. For a list of protocol-specified contraceptive methods, refer to [Appendix 6](#).
3. Co-infection with HCV, HIV, or HDV.
4. Evidence of hepatocellular carcinoma (e.g. as evidenced by recent imaging)
5. Any history of, or current evidence of, clinical hepatic decompensation (e.g., ascites, encephalopathy or variceal hemorrhage).
6. Abnormal hematological and biochemical parameters, including:
 - Hemoglobin < 10 g/dL
 - Absolute neutrophil count < 750/mm³

- Platelets $\leq 50,000/\text{mm}^3$
 - AST or ALT $> 10 \times \text{ULN}$
 - Total Bilirubin $> 2.5 \times \text{ULN}$
 - Albumin $< 3.0 \text{ g/dL}$
 - INR $> 1.5 \times \text{ULN}$ (unless stable on anticoagulant regimen)
7. Received solid organ or bone marrow transplant.
 8. Significant renal, cardiovascular, pulmonary, or neurological disease in the opinion of the investigator.
 9. Significant bone disease (e.g., osteomalacia, chronic osteomyelitis, osteogenesis imperfecta, osteochondroses), or multiple bone fractures.
 10. Malignancy within the 5 years prior to screening, with the exception of specific cancers that are cured by surgical resection (basal cell skin cancer, etc). Subjects under evaluation for possible malignancy are not eligible.
 11. Currently receiving therapy with immunomodulators (e.g. corticosteroids), investigational agents, nephrotoxic agents, or agents capable of modifying renal excretion.
 12. Known hypersensitivity to study drugs, metabolites, or formulation excipients.
 13. Current alcohol or substance abuse judged by the investigator to potentially interfere with subject compliance.
 14. Any other clinical condition or prior therapy that, in the opinion of the investigator, would make the subject unsuitable for the study or unable to comply with dosing requirements.
 15. Subjects on prohibited concomitant medications (See [Table 5-1](#)). Subjects on prohibited medications, otherwise eligible, will need a wash out period of at least 30 days.

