5.4. Prior and Concomitant Medications

Concomitant/previous medications **taken within 30 days of screening**, up to and including the date of the visit 4 weeks after discontinuation of study treatment, need to be recorded in the source documents and eCRFs.

Concomitant use of some medications including herbal/natural products/therapies and over the counter medications with TAF may result in PK interactions.

Should subjects have a need to initiate treatment with any excluded concomitant medication, including herbal/natural products/therapies, and over the counter medications, the Gilead Sciences Medical Monitor must be consulted prior to initiation of the new medication. In instances where an excluded medication is initiated prior to discussion with the Sponsor, the investigator must notify Gilead Sciences as soon as he/she is aware of the use of the excluded medication.

The following medications are excluded while subjects are participating in the study. These medications are **prohibited during the screening period and for a minimum of 30 days prior to the Baseline/Day 1** visit through the end of treatment:

- Nephrotoxic agents (e.g., aminoglycosides, amphoterecin B, vancomycin, cidofovir, foscarnet, cisplatin, pentamidine, cyclosporine, tacrolimus)
- Probenecid
- Agents that reduce renal function or compete for active tubular secretion with tenofovir (e.g., cidofovir, acyclovir, valacyclovir, ganciclovir, valganciclovir)

- Systemic chemotherapeutic agents, systemic corticosteroids (except short-term use of prednisone as a steroid burst [≤ 1 week of use], immunosuppressant, or immunomodulating agents
- Bisphosphonates
- Investigational agents (unless approved by Gilead Sciences)
- Medications excluded due to the potential for drug-drug interaction with TAF ([Table 5-1](#))

Treatment-experienced subjects (defined as subjects meeting all entry criteria [including HBV DNA and serum ALT criteria] and with ≥ 12 weeks of previous treatment with any nucleoside or nucleotide analogue) receiving oral antiviral treatment at Screening must continue their treatment regimen until the time of randomization/Baseline/Day 1, when it will be discontinued.

Table 5-1. List of Medications That Are Prohibited or to Be Used with Caution Due to the Potential for Drug-Drug Interaction with Study Medication

Medication Class	Prohibited Medications	Medications to be used with caution
Analeptic	Modafinil	

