Antiarrhythmics		Amiodarone, Quinidine: may increase concentration of TAF and/or TFV
Antibacterials		Clarithromycin: may increase concentration of TAF and/or TFV
Anticonvulsants		Carbamazepine, Oxcarbazepine, Phenobarbital, Phenytoin
Antifungals	Voriconazole	Itraconazole, Ketoconazole: may increase concentration of TAF and/or TFV
Antimycobacterials	Rifapentine, Rifabutin, Rifampin	
Calcium channel blockers		Diltiazem, Felodipine, Verapamil: may increase concentration of TAF and/or TFV
Digoxin		Digoxin: concomitant use may result in an increased or decreased level; use with caution and with appropriate monitoring of serum digoxin levels. Digoxin therapy should be initiated at the lowest dose, and the dose should be titrated to clinical response.
Herbal/Natural Supplements	St. John's Wort, Echinacea, Milk thistle (i.e., silymarin), Chinese herb sho-saiko-to (or Xiao-Shai-Hu-Tang)	

5.5. Accountability for Tenofovir Alafenamide (TAF), Tenofovir Disoproxil Fumarate (TDF) and Matched Placebos

The investigator or designee (i.e., pharmacist) is responsible for ensuring adequate accountability of all used and unused investigational medicinal product (IMP) kits and/or bottles. This includes acknowledgement of receipt of each shipment of IMP (quantity and condition). All used and unused IMP kits and/or bottles dispensed to subjects must be returned to the site.

Investigational product accountability records will be provided to each study site to:

- Record the date received and quantity of IMP kits and/or bottles
- Record the date, subject number, subject initials, the IMP kit number dispensed
- Record the date, quantity of used and unused IMP kits and/or bottles returned, along with the initials of the person recording the information

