7.6.2.2. Reporting Other Special Situations

All other special situation reports must be reported on the special situations report form and forwarded to the CRO Safety Dept within 24 hours of the investigator becoming aware of the situation. These reports must consist of situations that involve study IMP, but do not apply to concomitant medications. Special situations involving non-Gilead concomitant medications does not need to be reported on the special situations report form, however, for special situations that result in AEs due to a non-Gilead concomitant medication, the AE should be reported on the AE form. Any inappropriate use of concomitant medications prohibited by this protocol should not be reported as “misuse,” but may be more appropriately documented as a protocol deviation.

Refer to Section 7.3 and the CRF/eCRF completion guidelines for full instructions on the mechanism of special situations reporting.

All clinical sequelae in relation to these special situation reports will be reported as AEs or SAEs at the same time using the AE CRF/eCRF and/or the SAE report form. Details of the symptoms and signs, clinical management, and outcome will be reported, when available.

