4.4. Protocol Deviations

A listing will be provided for subjects in the Randomized Analysis Set who violated at least 1 inclusion or exclusion criterion. The listing will include the unmet criteria. A listing of subjects who received the wrong study treatment will also be provided.

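### The Week 48 per-protocol medication exclusion is an entry test, so subjects who start a prohibited drug during treatment stay in the set

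*SAP*

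**What the plan says.** SAP 3.1.4 excludes a subject from the Week 48 PP set on any of three grounds:

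- no on-treatment HBV DNA value in the Week 48 window, unless study drug was stopped for lack of efficacy;
- the medication rule, "Subjects who meet the exclusion criterion for receiving ongoing therapy with any of the prohibited medications listed in the clinical study protocol", with a reference to protocol Section 4.3 and Table 5-1;
- adherence to active study drug below the 2.5th percentile up to the Week 48 visit.

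Protocol Section 4.3 opens with "Subjects who meet any of the following exclusion criteria are not to be enrolled in this study". Its criterion 15 covers prohibited concomitant medication, points to Table 5-1 and adds "Subjects on prohibited medications, otherwise eligible, will need a wash out period of at least 30 days". Its criterion 11 covers current therapy with immunomodulators, investigational agents, nephrotoxic agents and agents that modify renal excretion.

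Protocol Section 5.4 sets a separate ban, from screening (and at least 30 days before baseline) to the end of treatment. It lists several drug classes and ends with "Medications excluded due to the potential for drug-drug interaction with TAF", pointing to Table 5-1, whose prohibited column includes "Rifapentine, Rifabutin, Rifampin". It foresees that an excluded drug may be started during the study and requires the sponsor to be told. Protocol 7.6.2.2 says that inappropriate use of prohibited medication "may be more appropriately documented as a protocol deviation".

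SAP 4.4 lists subjects who "violated at least 1 inclusion or exclusion criterion" and subjects who received the wrong treatment. SAP 6.1.3 gives the PP analysis the task of checking the robustness of the primary analysis.

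**The concern.** A PP set is meant to hold subjects whose treatment ran broadly as the protocol intended. Here the medication rule reaches only people who should not have been enrolled. It misses the violation that Section 5.4 itself anticipates, a prohibited drug started on treatment. If some of these subjects had HBV DNA or study-drug exposure altered by the other drug, the PP result would carry that disturbance instead of setting it aside. The protocol's analysis sets (8.2.1) include no PP set, so SAP 3.1.4 is its only definition.

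**Working it through.** **Step 1: which rule applies when.**

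| Text | When it is judged | Drugs covered |
|---|---|---|
| Protocol 4.3, criterion 15 | Entry | Table 5-1 |
| Protocol 4.3, criterion 11 | Entry | Immunomodulators, investigational agents, nephrotoxic agents, agents modifying renal excretion |
| Protocol 5.4 | Screening to end of treatment | Listed classes plus Table 5-1 |
| SAP 3.1.4 medication rule | Whether a Section 4.3 criterion is met | As Section 4.3 and Table 5-1 |
| SAP 4.4 listing | Whether an eligibility criterion was unmet | As Sections 4.2 and 4.3 |

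**Step 2: a test case.** A subject is eligible at Day 1, starts a rifamycin at Week 12, continues study drug with good adherence and has an HBV DNA value in the Week 48 window.

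- Week 48 HBV DNA ground: not met, because the value exists.
- Medication ground: not met, because no Section 4.3 criterion was met at entry.
- Adherence ground: not met, because it counts tablets of active study drug only (SAP 4.3.2).
- SAP 4.4 listing: not listed, because eligibility was satisfied and the treatment was as assigned.

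Neither Section 5.4 nor 7.6.2.2 requires study drug to stop, so the subject can reach Week 48 and stay in the PP set.

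**Step 3: size per subject.** Inputs are the planned China cohort of 100 TAF and 50 TDF (SAP 1.3) and an assumed response close to the planning rate of 91% (SAP 1.3). In whole subjects this is taken as 91/100 on TAF and 46/50 (92.0%) on TDF. Removing a subject lowers the denominator by 1, and lowers the numerator by 1 only if that subject responded.

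| Subject removed | TAF | TDF |
|---|---|---|
| Non-responder | 91/99 = 91.92%, +0.92 points | 46/49 = 93.88%, +1.88 points |
| Responder | 90/99 = 90.91%, -0.09 points | 45/49 = 91.84%, -0.16 points |

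**Step 4: how many subjects.** The documents give no rate of on-study prohibited use. For an assumed range of 2% to 5% of 150, the count is 0.02 × 150 = 3 to 0.05 × 150 = 7.5 subjects. For comparison, the adherence ground removes about 0.025 × 150 = 3.75.

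**The case against.** **The words on ongoing therapy could mean use during the study.** This is possible. But the operative test is meeting an exclusion criterion, with a Section 4.3 reference, and no period is given, whereas the adherence ground next to it names one. On either reading the sentence needs to say what is meant.

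**The rule is not confined to Table 5-1.** A reader might infer that it is, and that steroids, immunomodulators and investigational agents fall outside it. The documents do not support that. The rule cites Section 4.3 as a whole, and criterion 11 there names most of those classes. The gap is mainly one of timing, although a few Section 5.4 classes, such as bisphosphonates, appear in neither place.

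**The use is visible elsewhere.** Concomitant medications are coded, tabulated and listed (SAP 7.8; Table 65 and Listing 55 in Appendix 1), and protocol Section 6 requires deviations to be documented. This stands as far as visibility goes, but none of it changes PP membership.

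**No inference depends on the PP set.** This stands too. The SAP covers the China Week 48 analysis only. Sections 6.1.2 to 6.1.4 call for counts and percentages, with no margin, interval for the treatment difference or test. Protocol 8.5.2 describes the China analysis as a check of consistency with the overall population.

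**Excluding every Section 5.4 drug at any time would do harm.** This also stands. A fully adherent subject could be dropped for a drug with no stated bearing on HBV DNA. Bisphosphonates might be started because of bone loss, on which the trial expects the arms may differ (protocol 1.3.2), so that exclusion could depend on arm.

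**Conclusion.** The point holds as a gap in timing. SAP 3.1.4 tests medication use at entry, so on-treatment use contrary to Section 5.4 leaves PP membership unchanged and does not appear in the SAP 4.4 listing. This limits the set's stated robustness role and should be corrected, but the consequence is modest. The per-subject shifts rest on the assumed 91-92% response and the planned arm sizes, and the number of subjects affected is unknown.

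Three stronger conclusions might be drawn, and the documents support none of them:

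- *That each retained subject moves the rate by a full 1 point on TAF or 2 on TDF.* Those values are approached only for a non-responder. At the assumed rate most subjects are responders, for whom the shift is about 0.1 to 0.2 points.
- *That the effect falls mainly on the TAF arm.* Section 5.4 does describe the Table 5-1 drugs in terms of interaction with TAF. But the table's own title refers to study medication, and several of its caution entries name TAF and/or tenofovir, which both arms deliver. The protocol also rates TAF's potential for clinically relevant interactions as very low (1.2.2.3) and reports no dose effect on HBV DNA from 8 to 120 mg over 28 days (1.3.3). An unequal effect is possible but not shown.
- *That the non-inferiority conclusion is at risk.* The primary analysis here uses the full analysis set, and the non-China Week 48 analysis had already been conducted (SAP 2).

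**What to change.** - Keep the entry criterion in SAP 3.1.4 and add a PP exclusion for use, between Study Day 1 and the Week 48 HBV DNA sample, of a drug in the prohibited column of Table 5-1 or in a Section 5.4 prohibited class that could affect HBV DNA or TAF/tenofovir exposure (for example immunomodulators or investigational agents).
- Do not count use that Section 5.4 permits, such as the short prednisone burst, or drugs such as bisphosphonates that have no stated bearing on HBV DNA.
- Settle the drug list and any minimum duration by blinded review before subjects are assigned to analysis sets, which SAP 3.1 already places before unblinding.
- Add on-study prohibited medication use to the SAP 4.4 listing.

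The cost is one SAP bullet and one extension of a listing, from medication data that are already coded. The downside is a few more post-randomisation exclusions from the PP set.
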